11.6 Response Assessment

Participants will have evaluation of tumor burden at baseline (physical exam with tumor measurements, cross-sectional imaging as detailed above, RECIST and imRECIST reads of cross-sectional imaging), at 4 and 12 weeks after first T cell infusion, at 4 and 12 weeks after second infusion (if given), and then at discretion of treating oncologist (suggested frequency every 3-6 months). Patients with progressive disease on 4 week imaging but clinical stability may remain on study given the possibility of delayed clinical responses to immunotherapy. Imaging should also be performed if suspicion of progression. Imaging will be performed on a clinical basis with RECIST/imRECIST reads on a research basis. For skin/cutaneous tumors, representative/target tumors should (optionally) be photographed at key response assessment/measurement time points (day 14, 12 weeks, months 3, 6, 9, and 12 post infusion). Patients without measurable lesions will not be evaluable for response, but will be evaluable for safety endpoints.

Participants will have clinical pathology evaluation of tumor at baseline, at approximately 12 weeks after first T cell infusion, and if clinically suspected to have progression. Additional research biopsies are planned prior to T cell infusion, at 2 weeks post T cell infusion and at 12 weeks after second T cell infusion, and additional research tissue may be requested from clinical biopsies.

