Without treatment, metastatic MCC is near uniformly fatal. Spontaneous regressions have been reported in up to 1% of patients, therefore we will conservatively define a comparison response rate as 5% to allow for this and also for the possibility of very delayed checkpoint inhibitor response (although these have not been reported in MCC).^{6,7} There are no FDA-approved or known durably effective treatments for patients with advanced MCC tumors refractory to checkpoint blockade (hence the rationale for pursuing this population). Therefore, success in even a minority of patients would significantly advance the field.

Please see biostatistical section for further details on efficacy assessment and power calculation. In brief, in order to meet this endpoint, at least 3 of 16 patients will need an objective response (best response of partial response or complete response) by RECIST 1.1 criteria.⁷⁰

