5.2 Inclusion Criteria

5.2.1 Metastatic or unresectable VP-MCC

Participants must have metastatic or unresectable, histologically confirmed virus-positive MCC. Confirmation of diagnosis must be or have been performed by internal pathology review of initial or subsequent biopsy or other pathologic material at Fred Hutch.

Approximately 80% of MCCs are caused by MCPyV T Antigens,¹⁶ and the treatment is expected to only be effective in this population. Merkel cell polyomavirus positivity may be established through one of two means: positive Merkel cell polyomavirus T antigen serology (preferred) or immunohistochemistry of a primary or metastatic MCC tumor lesion (if T antigen seronegative).

MCPyV T Antigen serology will be performed with the AMERK assay run through the University of Washington Medical Center Laboratory Medicine Clinical Immunology Laboratory (<https://testguide.labmed.uw.edu/public/view/AMERK>).^{73,74} Positivity will be defined as a Merkel oncoprotein antibody titer (MSCTT) of ≥ 75 standard titer units (STU) at any time point from initial diagnosis onward. Patients with negative T antigen serology but MCPyV positive tumor by other methodologies will be considered for additional MCPyV testing as clinically appropriate, as the T antigen serology assays are highly specific^{73,75} but incompletely sensitive for MCPyV status.⁷³ In this case, immunohistochemistry of any tumor lesion will be performed with the CM2B4 Merkel cell polyomavirus T antigen antibody⁷⁶. Expression of MCPyV in at least 10% of tumor cells will be considered positive. CM2B4 staining performed at any point clinically and at any clinical laboratory may be accepted. However, if CM2B4 staining has not been previously performed by a clinical pathology laboratory as part of MCC diagnostic workup, it will be performed in a clinical diagnostic pathology laboratory at UW/Fred Hutch as per standard staining protocols. Persons are not required to have both CM2B4 positivity and seropositivity; either will be acceptable confirmation of viral status and if one negative and the other positive the patient will remain eligible provided other criteria are met.

5.2.2 Previous treatment with a PD-1 axis inhibitor or contraindication to treatment with a PD-1 axis inhibitor

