13. STATISTICAL CONSIDERATIONS

13.1 Sample size and Power

Our study is a phase I/II, non-blinded interventional trial. Our target sample size is up to 16 patients (8 per year/2 years). This target is chosen for three reasons: it is achievable from an enrollment standpoint (our clinic sees between 15-20 potentially eligible patients per year), it is logistically possible from a funding and cell processing facility standpoint, and it allows >80% power to observe a statistically significant (at one-sided 0.05 level) efficacy signal that is clinically meaningful. (see below for details). With the eligibility expansion, we expect roughly 12 patients will receive a PD1 checkpoint inhibitor. For some analyses, all 16 patients will be analyzed, yet some analyses will be restricted to patients who receive a PD1 checkpoint inhibitor. See below for the impact of this on statistical power.

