13.3 Primary Endpoint: Efficacy

13.3.1 Definition of response

Irradiated and non-irradiated lesions will be separately tracked but response determined in totality. As indicated, patients who will be evaluated for this endpoint will have at least one trackable lesion by response evaluation criteria in solid tumors (RECIST) 1.1. Response will be defined as best overall response by RECIST 1.1 of complete or partial response for patients with at least one measurable lesion.

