13.3.2 Definition of success and power of success

Responses to alternative therapies in this population of patients with advanced MCC resistant to PD1-axis blockade are rare, and we therefore will use a 5% response rate as the fixed benchmark upon which we hope to improve with the proposed treatment. If the true response rate with TCR-transduced cells is 25%, 16 patients yield 84% power to detect a statistically significantly improved response rate (one-sided .05) over the fixed rate of 5%. Three or more responses among 16 pts would occur with probability .04 if the true response rate is 5%, so if three or more patients respond (an observed response rate of at least 19%), we will conclude that this regimen is potentially efficacious and worthy of further

study. If power is instead assessed among the anticipated 12 patients who will receive a checkpoint inhibitor, the statistical power is reduced to 78%.

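### The 3-response rule and its power assume that all 16 patients are evaluable for response, but Section 5 does not require a measurable lesion

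*Combined protocol and SAP*

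**What the plan says.** Eligibility. Section 5.2.1 sets the disease requirement: "Participants must have metastatic or unresectable, histologically confirmed virus-positive MCC". Section 5.2.2 adds progression on or after a PD-1 axis inhibitor, biopsy-proven residual disease after it, or a contraindication to that class. None of the criteria in 5.2 or 5.3 mentions measurable disease. Under 11.3, relapsed disease may be documented by imaging, biopsy or both.

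Endpoint. Section 11.6 states: "Patients without measurable lesions will not be evaluable for response, but will be evaluable for safety endpoints". Section 13.3.1 repeats the restriction: "patients who will be evaluated for this endpoint will have at least one trackable lesion". Section 6.4.1 adds a second condition, that a product counts for response only if it holds 10% or more of the scheduled transgenic CD8+ dose; smaller doses may still be given.

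Rule and sample size. Section 13.1: "Our target sample size is up to 16 patients (8 per year/2 years", and of that number, "it allows >80% power to observe a statistically significant (at one-sided 0.05 level) efficacy signal that is clinically meaningful". Section 3.1.2: "at least 3 of 16 patients will need an objective response". Section 13.3.2: "If the true response rate with TCR-transduced cells is 25%, 16 patients yield 84% power to detect a statistically significantly improved response rate". The same section puts the chance of three or more responses among 16 at .04 when the true rate is 5%. It also gives 78% power for the 12 patients expected to receive a checkpoint inhibitor. That is the only power quoted for fewer than 16, and it has nothing to do with measurability. The documents contain no replacement rule, no inflation of the 16, and no rule for a smaller evaluable number.

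**The concern.** A site that follows Section 5 to the letter can enrol and treat a patient who cannot count towards the primary efficacy endpoint. That patient uses one of at most 16 places. The success rule still asks for three responders, now from fewer patients who are able to respond. The risk is a missed signal: an active regimen is less likely to reach three responses than the protocol states. With so few patients, even one or two such cases change the power noticeably. The reported rate is also left open, because the plan does not say whether three responders among 14 evaluable patients are to be reported as 3/14 (21%) or 3/16 (19%).

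**Working it through.** **Inputs.** From 13.1 and 13.3.2: n = 16, one-sided 0.05, null rate 5%, alternative 25%, success at 3 or more responses. The synopsis attaches a power of 0.84 to a 20% rate; I use the 25% of 13.3.2, which is the rate that reproduces the figure. The number of non-evaluable patients is not in the documents, so I show 0 to 3 as an assumed range.

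**1. The plan's own power.** One-sample normal approximation:

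power = Φ[(0.20·√n − 1.645·√(0.05·0.95)) / √(0.25·0.75)]

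- n = 16: Φ[(0.800 − 0.3585)/0.4330] = Φ(1.02) = 84.6% (stated 84%).
- n = 12: Φ[(0.6928 − 0.3585)/0.4330] = Φ(0.77) = 78.0% (stated 78%).

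Both stated powers are therefore consistent with this approximation.

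**2. The plan's own error rate and the exact power of its rule.** With X binomial(16, p), P(X ≥ 3) = 1 − P(0) − P(1) − P(2).

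- p = 0.05: 1 − 0.4401 − 0.3706 − 0.1463 = 0.043 (stated .04).
- p = 0.25: 1 − 0.0100 − 0.0535 − 0.1336 = 0.803.

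The stated error is the exact binomial value, but the stated power is not. The exact power of 3 or more out of 16 is 80.3%.

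**3. Fewer evaluable patients.**

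| Evaluable | Type I error, ≥3 | Exact power at 25%, ≥3 | Type I error if cut-off were 2 | Normal-approximation power |
|---|---|---|---|---|
| 16 | 0.043 | 0.803 | 0.189 | 0.846 |
| 15 | 0.036 | 0.764 | 0.171 | 0.832 |
| 14 | 0.030 | 0.719 | 0.153 | 0.816 |
| 13 | 0.025 | 0.667 | 0.135 | 0.799 |

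A cut-off of 2 is not available: even with 8 evaluable patients its type I error is 0.057. Three is thus the minimum for every number from 8 to 16. Each lost patient costs about 4 to 5 points of exact power (0.803 − 0.764 = 0.039; 0.764 − 0.719 = 0.045; 0.719 − 0.667 = 0.052).

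**4. Does the choice of denominator matter to the test?** No. If non-evaluable patients are kept in a denominator of 16 as non-responders, success still means three responses among those who can respond, so both error rates are those in the table. The choice affects only the reported rate and its interval.

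**The case against.** Admitting these patients looks deliberate. Section 11.6 foresees them and keeps them for safety, which is also a primary objective, and they contribute to persistence and survival. That stands. What is missing is an allowance for them in the efficacy sample size.

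The number affected may be zero or one. Patients must have metastatic or unresectable disease, baseline cross-sectional imaging is planned, and the target population has mostly progressed on treatment. That also stands, and it is why the loss is given as a range. A reader might infer from 5.2.2 that biopsy-proven residual disease alone is enough for entry. It is not, because 5.2.1 applies as well.

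A reader might also infer that one non-measurable patient is what pushes the trial below 80%. The crossing owes more to step 2: the exact rule starts at 80.3%, not 84%. On the protocol's own approximation, power stays above 80% down to 14 evaluable patients. The exact figure is the right one for a rule that counts responders, and the loss per patient remains either way.

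Finally, a reader might infer a raised risk of a false positive. The table shows the opposite. The protocol also claims only that a positive result makes the regimen worth further study, and it openly accepts a stated 78% in the checkpoint-inhibitor subset. This limits the seriousness of the point, but does not make the power claimed in 13.1 correct for fewer than 16 evaluable patients.

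**Conclusion.** The point holds as a gap between eligibility and the efficacy sample size. The power above 80% in 13.1 is reached by the stated rule only if all 16 patients are evaluable for response, and neither Section 5 nor any replacement rule ensures this. If one to three patients are not evaluable, exact power at a true 25% rate is 0.764 to 0.667, against 0.803 with none lost; type I error stays below 0.05 throughout. This rests on the 25% alternative of 13.3.2, on independent responses, and on an assumed number of non-evaluable patients, since the documents give none. The 10% dose condition in 6.4.1 can reduce the evaluable number in the same way. The gap between the stated 84% and the exact 80.3% is a separate matter, but it explains why there is no margin to absorb even one loss.

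**What to change.** Add to 5.2, for all patients in both parts, a requirement of one or more RECIST 1.1 measurable lesions at baseline. Limiting it to part II would not be enough: if the three part I patients had no measurable lesion, 13 evaluable patients would remain, with power 0.667.

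The cost is that a few patients with only non-measurable disease could not enter. The baseline RECIST read is already planned in 11.3, but the imaging there is timed to the infusion, while 4.3 places enrolment just before leukapheresis. The read may therefore have to be done earlier. Section 13.1 reports 15 to 20 potentially eligible patients a year against 8 needed, which suggests room, although the text does not say whether HLA type and viral status have already been applied to that count.

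If patients without measurable disease are to be kept for safety, restate 3.1.2, 13.1 and 13.3.2 as three or more responders among response-evaluable patients. Define that set in one place, including the 10% dose condition of 6.4.1, and state the denominator for the reported rate. Replace the 84% with exact power for 13 to 16 evaluable patients (0.667, 0.719, 0.764, 0.803). This costs only text, but it accepts the lower power openly. The measurable-lesion criterion alone does not remove losses through 6.4.1, so the definition of the evaluable set is worth adding in either case.

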11.7 Participant discontinuation of active treatment

A patient will no longer be able to receive active treatment on study (T cells, avelumab or pembrolizumab, or class I MHC upregulation) for any of the reasons listed below.

- Progressive disease or development of new metastasis requiring urgent change in treatment after the second T cell infusion. Patients with progressive disease on 4 week imaging but clinical stability may remain on study given the possibility of pseudoprogression and delayed clinical responses to immunotherapy.
- The participant withdraws consent
- Patient death
- Occurrence of pregnancy
- Participation in another therapeutic trial during the treatment duration of this trial
- Occurrence of an exclusion criterion, which is clinically relevant and affects the subject's safety, if discontinuation is considered necessary by the Investigator or Sponsor
- A patient will no longer be eligible to receive additional therapy if the PI or his designee determines that additional T cell infusions are not in the best interest of the patient
- Occurrence of any non-pre-existing grade 3 or higher AEs / repetitive Grade 2 Adverse events deemed related to the treatment, except for expected, transient toxicities associated with avelumab, pembrolizumab, interferon gamma and T cell infusion.

- Cytokine release syndrome requiring pressors for >24 hours or tocilizumab
- The reasons for premature discontinuation must be recorded on the case report form. The patient may re-enter the study after premature discontinuation only by approval of the PI

Unless there is withdrawal of consent or death, the patient will transition to the LTFU phase of study.

11.8 Long-term follow-up (LTFU)

Enrolled patients who receive FH-MCVA2TCR will be asked to participate in LTFU according to guidelines set forth by the FDA's Biologic Response Modifiers Advisory Committee that apply to gene transfer studies. Current recommendations from the FDA suggest a minimum of 15 years of follow-up. Annual blood work (20 cc lavender top/10 cc serum separator) will be recommended to be used for RCL (replication competent lentivirus; required), persistence, and immune monitoring (optional). Medical records will be requested at least annually to determine long term outcomes. Should the participant develop a late relapse, a 50 cc blood draw and/or leftover/excess biopsy tissue (fresh and/or archival) will be requested for evaluation as to mechanisms of late relapse. Recommendations will be made for an autopsy to be conducted if the research participant dies.

12. ADVERSE EVENT REPORTING

12.1 Adverse Event Definitions

- **Adverse Event**

An Adverse Event (AE) is any untoward medical occurrence in a clinical investigation patient administered a medicinal product; the event does not necessarily have a causal relationship with study drug administration or usage. An adverse event can therefore be any unfavorable and unintended sign (including an abnormal laboratory finding), symptom, or disease temporally associated with the use of a medicinal product, whether or not considered related to the medicinal product.

- **Serious Adverse Event**

A serious adverse event (SAE) is defined as an untoward medical occurrence that results in any of the following outcomes:

1. Death.
2. Life-threatening situation (i.e., with an immediate risk of death from the event as it occurred but not including an event that, had it occurred in a more serious form, might have caused death).
3. In-patient hospitalization or prolongation of existing hospitalization. Inpatient hospitalization comprises formal admission to a hospital for medical reasons, for any length of time, whether or not hospitalization extends overnight. However, hospital admissions for administration of the study drug, procedures required by the study protocol, or tumor-related diagnostic procedures are not considered serious.
4. Persistent or significant disability/incapacity or substantial disruption of the ability to conduct normal life functions.
5. Congenital anomaly/birth defect.
6. An important medical event that requires intervention to prevent one of the above outcomes.

- **Unexpected Adverse Event**

An unexpected adverse event is defined as an event that has a nature or severity, or frequency that is not consistent with the investigator brochure, protocol, or consent form. Please see **Section 12.6** for expected toxicities.

12.2 Monitoring and Recording Adverse Events

Adverse events will be assessed by the investigator or qualified designee and recorded in the CRFs. The investigator should attempt to establish a diagnosis of the event on the basis of signs, symptoms and/or other clinical information. In such cases, the diagnosis should be documented as the adverse event and/or serious adverse event and not described as the individual signs or symptoms. The following information should be recorded:

- Description of the adverse event using concise medical terminology
- Description as to whether or not the adverse event is serious
- The start date (date of adverse event onset)
- The stop date (date of adverse event resolution or return to baseline)
- The severity (grade) of the adverse event
- A description of the potential relatedness of the adverse event to study drug or a study procedure, as determined by the PI
- Expectedness of the adverse event based on prior observed and documented adverse events, as determined by the PI
- The outcome of the adverse event

12.3 Grading of the Severity of an Adverse Event

Immune effector cells are recognized to have a unique set of toxicities associated with T cell activation including cytokine release syndrome (CRS) and neurotoxicity/ICANS. In general, TCR-T therapies have not been described to be associated with CRS and neurotoxicity to the same severity and extent that certain CAR-T therapies have. However, given that the underlying mechanism is T cell activation, CRS and neurotoxicity management scales designed for CAR-T are reasonably applied to TCR-T. Therefore, for grading cytokine release syndrome and neurotoxicity associated with TCR-T cells we will utilize the recently published international consensus guidelines: ASTCT Consensus Grading for Cytokine Release Syndrome and Neurologic Toxicity Associated with Immune Effector Cells (Lee et al; 2019).⁷⁹ Individual components of CRS (e.g. fever, hypotension, hypoxia) will be graded as part of the CRS score, and will not count as separate adverse events, so long as the timing and clinical picture is consistent with cytokine release syndrome.

All other AEs will be graded in severity according to the NCI Common Terminology Criteria for Adverse Events ([CTCAE Version 5.0](#)). If a CTCAE criterion does not exist, the investigator should use the grade or adjectives: Grade 1 (mild), Grade 2 (moderate), Grade 3 (severe), Grade 4 (life-threatening), or Grade 5 (fatal) to describe the maximum intensity of the adverse event.

12.4 Attribution of Adverse Event

Association or relatedness to the study agent will be assessed by the PI as follows:

Definite (must have all 4)	
 • Has a reasonable temporal relationship to the intervention
---------------------------------------	--

	
 • Could not have readily been produced by the patient's clinical state or have been due to environmental or other interventions • Follows a known pattern of response to intervention • Disappears or decreases with reduction in dose or cessation of intervention and recurs with re-exposure
Probable (must have 3)	
 • Has a reasonable temporal relationship to the intervention • Could not have readily been produced by the patient's clinical state or have been due to environmental or other interventions • Follows a known pattern of response to intervention • Disappears or decreases with reduction in dose or cessation of intervention
Possible (must have 2)	
 • Has a reasonable temporal relationship to the intervention • Could not have readily been produced by the patient's clinical state • Could not readily have been due to environmental or other interventions • Follows a known pattern of response to intervention
Unlikely (must have 2)	
 • Does not have a temporal relationship to the intervention • Could readily have been produced by the patient's clinical state • Could have been due to environmental or other interventions • Does not follow a known pattern of response to intervention • Does not reappear or worsen with reintroduction of intervention

For general AE assessment, an AE is considered related if it is assessed as definitely, probably, or possibly related; unrelated if it is assessed as unlikely related or unrelated.

For determination of IND safety reporting, AE attribution will be assessed according to the suspected adverse reaction definition described in 21 CFR 312.32 as an AE for which there is a reasonable possibility that the drug caused the adverse event where “reasonable possibility” means there is evidence to suggest a causal relationship between the drug and the AE. The IND Sponsor will report suspected adverse reactions that are both serious and unexpected to the FDA as an IND safety report, in accordance with regulations under 21 CFR 312.32.

